9.6 Response Criteria

9.6.1 Evaluation of Target Lesions

0.6.1 Evaluation of Target 1	Lesions
Complete Response (CR):	Disappearance of all target lesions
Partial Response (PR):	At least a 30% decrease in the sum of the longest diameter (LD) of target lesions, taking as reference the baseline sum LD.
	Daseille still LD.
Progressive Disease (PD):	At least a 20% increase in the sum of the LD of target lesions, taking as reference the smallest sum LD recorded since the treatment started or the appearance of one or more new lesions.
Stable Disease (SD):	Neither sufficient shrinkage to qualify for PR nor sufficient increase to qualify for PD, taking as reference the smallest sum LD since the treatment started.

9.6.2 Evaluation of Non-Target Lesions

Complete Response (CR):	Disappearance of all non-target lesions and *normalization of tumor marker level.
Incomplete Response/ Stable Disease (SD):	Persistence of one or more non-target lesion(s) and/or maintenance of tumor marker level above the normal limits.
Progressive Disease (PD):	Appearance of one or more new lesions and/or unequivocal progression of existing non-target lesions.
Although a clear progression circumstances the opinion of	n of "non-target" lesions only is exceptional, in such f the investigator will prevail.
*Note: If tumor markers are normalize for a patient to be	e initially above the upper normal limit, they must considered in complete clinical response.

9.6.3 Evaluation of Best Overall Response

The best overall response is the best response recorded from the start of the treatment until disease progression/recurrence (taking as reference for progressive disease the smallest measurements recorded since the treatment started). The patient's best response assignment will depend on the achievement of both measurement and confirmation criteria.

Target Lesions	Non-Target Lesions	New Lesions	Overall Response
CR	CR	No	CR
CR	Incomplete response/SD	No	PR
PR	Non-PD	No	PR
SD	Non-PD	No	SD
PD	Any	Yes or No	PD
Any	PD	Yes or No	PD
Any	Any	Yes	PD

Notes:

Patients with a global deterioration of health status requiring discontinuation of treatment without objective evidence of disease progression at that time should be classified as having "symptomatic deterioration." Every effort will be made to document the objective progression.

In some circumstances, it may be difficult to distinguish residual disease from When the evaluation of complete response depends on this determination, the residual lesion will be investigated (fine needle aspirate/biopsy if possible) before confirming the complete response status.

9.7 Confirmatory Measurement/Duration of Response

9.7.1 Confirmation

To be assigned a status of PR or CR, changes in tumor measurements must be confirmed by repeat assessments that will be performed no less than 4 weeks after the criteria for response are first met. In the case of SD, follow-up measurements must have met the SD criteria at least once after study entry at a minimum interval of not less than 8 weeks.

9.7.2 Duration of Overall Response

The duration of overall response is measured from the time measurement criteria are met for CR or PR (whichever is first recorded) until the first date that recurrent or progressive disease is objectively documented (taking as reference for progressive disease the smallest measurements recorded since the treatment started).

The duration of overall CR is measured from the time measurement criteria are first met for CR until the first date that recurrent disease is objectively documented.

9.7.3 Duration of Stable Disease

Stable disease is measured from the start of the treatment until the criteria for progression are met, taking as reference the smallest measurements recorded since the treatment started.

10. Removal of Patients from Study/Off Study Criteria

In the absence of treatment delays due to adverse events, treatment may continue until one of the following criteria applies:

a) Disease progression/relapse during active treatment,

b) Intercurrent illness that prevents further administration of treatment,

c) Unacceptable adverse event(s).

- d) In the event of any drug-related life-threatening toxicity or laboratory abnormality the patient will be withdrawn from further treatment,
- e) Patient decides to withdraw from the study,

[figure not shown]
f) Noncompliance with treatment plan,

- g) General or specific changes in the patient's condition render the patient unacceptable for further treatment in the judgment of the investigator, or
- h) Protocol violation any patient found to have entered this study in violation of the protocol might be discontinued from the study at the discretion of the Principal Investigator.

11. Laboratory Evaluations and Procedures/Correlative Studies

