7.3 Treatment Administration

Treatment will require daily oral administration of medications on an outpatient basis.

Treatment may be delayed for up to two weeks for recovery from Grade 3 or 4 adverse events. If patients do not recover within two weeks, the patient will be removed from study.

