living	2 nd occurrence 3 rd occurrence	As for first occurrence, but upon resuming sorafenib treatment, decrease dose to the next lower dose level indefinitely Decision whether to discontinue sorafenib treatment should be made based on clinical judgement and patient preference

^{*}Patients who develop grade 3 fever/chills, grade 3 elevation of hepatic transaminases with ALT and AST < 10X ULN, grade 3 hyperlipasemia or hyperamylasemia without clinical or other evidence of pancreatitis, grade 3 leukopenia, or grade 3/grade 4 lymphopenia may continue study treatment without interruption at the discretion of the investigator.

Phase I/II Trial of Letrozole	and Sorafenib	as First-Line Therapy in Postmenopau	sal
Women with Hormone Receptor-Pos	ifive Locally Advance	ed or Metastatic Breast Cancer	
PI:			

Table 7.5.2.2 Dose Modification for Sorafenib Associated Non- Hematologic Toxicity

Toxicity	Grade 1	Grade 2	Grade 3	Grade 4
Non-	Continue at the	Continue at the	Withhold dose until	Withhold dose until
hematologic	same dose level.	same dose level.	toxicity is grade ≤ 1 ,	toxicity is grade ≤ 1 ,
			then resume treatment	then reduce dose to the
			at the same dose level.	next lower dose level
5-			If patient experiences	and resume treatment,
			a second grade 3	or discontinue at the
			toxicity, withhold	discretion of the
			dose until toxicity is	principal investigator
			grade ≤ 1 , then reduce	after discussion with
		* s (dose the next lower	study sponsor.
			dose level and resume	
			treatment.	If toxicity does not
				resolve within 2 weeks
			If toxicity does not	patient will discontinue
			resolve within 2	treatment.
			weeks patient will	
			discontinue treatment.	If a second toxicity
				occurs the patient will
				discontinue treatment.

Phase I/II Trial of Letrozole	and Sorafenib	as First-Line Therapy in Postmenopaus	al
Women with Hormone Receptor-Pos.	itive Locally Advanced	d or Metastatic Breast Cancer	
PI:			

Table 7.5.2.3 Dose Modification for Sorafenib Associated HematologicToxicity

Day 1 of Any Cycle	ANC < 1200/µL and/or platelets < 100,000 /µL	Hold Treatment
* CBCs should be repeated weekly until	If count recovers within 1 week	Resume treatment at full dose
recovery	If count recovers within 2 weeks	Reduce 1 dose level for all subsequent cycles
	If count does not recover within 2 weeks	Discontinue protocol treatment

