Anytime during treatment	Febrile episode (> 38.5°C) accompanied by ANC count < 1200/μL	Reduce 1 dose level for all subsequent cycles.
	A subsequent febrile neutropenic event	Discontinuation of protocol therapy

Table 7.5.2.3.A Dose Modification for Sorafenib Associated HematologicToxicity

Toxicity	Grade 1	Grade 2	Grade 3	Grade 4
Hematologic toxicities not listed above	Continue at the same dose level.	Continue at the same dose level.	Withhold dose until toxicity is grade ≤ 2 , then resume treatment at the same dose level. If patient experiences a second grade 3 toxicity, withhold dose until toxicity is grade ≤ 2 , then reduce dose to the next lower dose level and resume treatment.	Withhold dose until toxicity is grade ≤ 2, then reduce dose to the next lower dose level and resume treatment, or discontinue at the discretion of the principal investigator.

Phase I/II Trial of Letrozole	and Sorafenib	as First-Line Therapy in Postmenopausal
Women with Hormone Receptor-Pos	ifive Locally Advanced	or Metastatic Breast Cancer
PI:		

Table 7.5.2.4 Management of Treatment Emergent Hypertension

Grade	Management/Next Dose
Grade 1	Consider increased BP monitoring
Grade 2 asymptomatic and diastolic BP < 110 mm Hg	Begin anti-hypertensive therapy and continue agent.
Grade 2 symptomatic and/or persistant OR Diastolic BP ≥ 110 mm Hg OR	Agent should be held until symptoms resolve and diastolic $BP \le 100 \text{ mm Hg}$; also treat patient with antihypertensives and when agent is restarted reduce by 1 dose level.
Grade 3	If diastolic BP is not controlled (\leq 100 mm Hg) on the rapy reduce another dose level.
Grade 4	Discontinue therapy.

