An increased incidence of hypertension was observed in sorafenib-treated patients. Hypertension was usually mild to moderate, occurred early in the course of treatment, and was amenable to management with standard antihypertensive therapy. Blood pressure should be monitored monitored weekly for the first 6 weeks of therapy and then on a regular basis and treated, if required, in accordance with standard medical practice. In cases of severe or persistent hypertension, or hypertensive crisis despite adequate antihypertensive therapy, permanent discontinuation of sorafenib should be considered. Permanent discontinuation of therapy due to hypertension occurred in 1 of 451 sorafinib patients.

An increase in the risk of bleeding may occur following sorafenib administration. The incidence of severe bleeding events is uncommon. If any bleeding event necessitates medical intervention, it is recommended that permanent discontinuation of sorafenib be considered.

Temporary or permanent discontinuation of sorafenib should be considered in patients who develop cardiac ischemia and/or infarction.

Sorafenib therapy should be discontinued in patients with gastointestinal perforation.

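### Section 10(d) requires withdrawal after a drug-related life-threatening toxicity, but the Grade 4 cells of Tables 7.5.2.2 and 7.5.2.3.A let a site reduce sorafenib and resume

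*Combined protocol and SAP*

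**What the plan says.** Section 10 lists the reasons for ending treatment. Item (d) reads: "In the event of any drug-related life-threatening toxicity or laboratory abnormality the patient will be withdrawn from further treatment". The list's lead-in says that "treatment may continue until one of the following criteria applies", but the same sentence opens with a condition that limits it to situations with no treatment delay for adverse events.

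Section 7.5.2 tells the site how to handle sorafenib toxicity:

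- **Table 7.5.2.2**, titled "Dose Modification for Sorafenib Associated Non- Hematologic Toxicity". At Grade 4 the site holds sorafenib until the toxicity is grade 1 or lower, then drops one dose level and restarts. Alternatively, the principal investigator may choose to discontinue after talking to the sponsor. Stopping is compulsory only if the toxicity has not resolved in 2 weeks or a second toxicity occurs.
- **Table 7.5.2.3.A**, for sorafenib-associated hematologic toxicities not covered by Table 7.5.2.3. At Grade 4 the site holds sorafenib until grade 2 or lower, then may "reduce dose to the next lower dose level and resume treatment, or discontinue at the discretion of the principal investigator".
- **The footnote after Table 7.5.2.1**: patients with "grade 3/grade 4 lymphopenia may continue study treatment without interruption at the discretion of the investigator".

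Section 7.3 allows a delay of up to two weeks for Grade 3 or 4 events: "If patients do not recover within two weeks, the patient will be removed from study". Section 7.7 says: "Temporary or permanent discontinuation of sorafenib should be considered in patients who develop cardiac ischemia and/or infarction". Its next sentence is firmer: "Sorafenib therapy should be discontinued in patients with gastointestinal perforation".

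**The concern.** Some events fall under both rules: they are sorafenib-related, are Grade 4, and put the patient at risk of death. For these, Section 10(d) gives the site one permitted action, while the table offers two and names resumption first. Site staff adjusting a dose are likely to turn to the table, and nothing in it sends them to Section 10.

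What is at stake is re-exposure to sorafenib in a patient who has just survived a life-threatening reaction to it, in a trial whose own removal rule says she should stop. The trial runs at several sites, so different sites could also act differently on the same event.

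**Working it through.** There is no figure in the plan to reproduce on this point. The check is a comparison of texts.

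**Step 1: do the rules overlap?** Section 10(d) needs two things, drug-relatedness and threat to life. The titles of both tables restrict them to sorafenib-associated toxicity, so the first is met. For the second, Section 8.1.4 defines life-threatening as the patient being at risk of death during the event. Nothing in either Grade 4 cell removes such events, so the overlap is not empty.

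**Step 2: do the actions differ in the overlap?**

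- Section 10(d): withdraw, with no condition about recovery.
- Table 7.5.2.2, Grade 4: hold, reduce and resume, or discontinue by choice.
- Table 7.5.2.3.A, Grade 4: the same structure, with recovery set at grade 2 or lower.

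They differ. Discontinuing satisfies every text; resuming satisfies the tables and breaches Section 10(d).

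**Step 3: does any text rank the rules?** None does. The Section 10 lead-in does not settle the matter, because its opening condition sets aside cases with adverse-event delays, and these are the hold-and-recover patients in question. The mandatory wording of item (d) itself is the only support for treating it as controlling.

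**Step 4: does a safeguard catch the patient?** Take a first drug-related life-threatening event that recovers in, say, ten days.

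- Two-week rule (Section 7.3; Table 7.5.2.2): not triggered, because she recovered.
- Second-toxicity stop (Table 7.5.2.2): not triggered, because this is a first event.
- Sponsor discussion (Table 7.5.2.2): attached to the discontinuation option; whether it also applies to resuming is unclear, and it dictates no outcome.
- Recheck before each cycle (Section 7.1): re-applies the inclusion criteria of Section 5.1, including performance status and laboratory limits. It can block some restarts, but does not re-apply the exclusions in Section 5.2, where recent myocardial infarction and unstable angina sit.
- Sections 10(b), (c) and (g): allow stopping on grounds that call for judgment.
- SAE reporting within 24 hours (Section 8.1.7): informs others but does not direct the site's action.

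None of these requires her to stop.

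**Step 5: where else is the exception missing?** Section 7.3 has the same gap. So does Table 7.5.2.3, where low counts that recover within one week lead back to full dose and a first febrile neutropenic episode leads only to a reduction. In Section 7.7, the cardiac, bleeding and hypertensive-crisis sentences only ask that discontinuation be considered. By contrast, Grade 4 hypertension in Table 7.5.2.4 and perforation in Section 7.7 both call for stopping, in line with Section 10(d).

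**Step 6: size.** The documents give no rate for drug-related life-threatening events. As an illustration for one route only, Section 12.1 lists myocardial ischemia and infarction, of any severity, at 0.1% to under 1%. For 64 patients that is 64 × 0.001 = 0.064 to under 64 × 0.01 = 0.64. This is not an upper bound: 64 is the number within which Section 16.2 expects evaluable accrual to stay, whereas Section 8 counts anyone given one dose as evaluable for toxicity.

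**The case against.** The best reply is that there is no true contradiction. Section 10(d) is mandatory, each table cell permits discontinuation, and a site can obey everything by stopping. On that view only a cross-reference is missing. It is true that compliance is possible. But the cells permit it without requiring it, no sentence gives Section 10(d) precedence, and resuming is the action the cells name first. A site that resumed could point to the table in its defence.

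A second reply is that the tables have a proper use of their own. This stands. A reader might infer that every Grade 4 event triggers Section 10(d), so that the Grade 4 cells can never apply. The documents do not support that: they cite CTCAE version 3.0 without reproducing its grade definitions, and the lymphopenia footnote shows that a Grade 4 laboratory value may be compatible with continuing.

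A third reply concerns Section 7.7, and it largely stands. The cardiac sentence is guidance, and it covers ischemia of any severity and cause. A reader might take its contrast with the perforation sentence as deliberate permission to restart after a life-threatening cardiac event. The text does not show that intent, because a temporary stop has legitimate uses outside Section 10(d).

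Finally, Section 10(d) does not cite Section 8.1.4, so using that definition here is an interpretation, though it is the only definition the protocol gives.

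**Conclusion.** The conflict is real for the Grade 4 cells of Tables 7.5.2.2 and 7.5.2.3.A. As written, they allow sorafenib to be restarted after a first drug-related life-threatening event that recovers within two weeks, where Section 10(d) requires withdrawal. Section 7.3 and Table 7.5.2.3 share the omission; the Section 7.7 sentences do so more weakly.

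The conclusion assumes that life-threatening in Section 10(d) carries the Section 8.1.4 meaning. It does not depend on how many Grade 4 events meet it.

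Few patients are expected to be affected, and the number cannot be estimated from the documents. A reader might infer some distortion of the clinical benefit rate; nothing in the documents supports one, and none is claimed. The change should be made because re-exposure could be grave and the correction costs very little.

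**What to change.** Put one precedence sentence at the start of Section 7.5.2, and repeat or reference it in Sections 7.3, 7.7 and 10:

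*Any drug-related event that places the patient at risk of death requires withdrawal from further treatment under Section 10(d), regardless of recovery; the delay, dose-modification and supportive-care rules in Section 7 apply only to other events.*

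Add a short pointer to it in the Grade 4 cells of Tables 7.5.2.2 and 7.5.2.3.A. A single general rule is better than exceptions in selected places, which could suggest that the places left unmarked are exempt. The tables keep governing Grade 4 events without risk of death, such as lymphopenia. Since the sentence fixes the meaning of life-threatening in Section 10(d), the sponsor should confirm that this is the meaning intended.

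The cost is a wording amendment. Assessments, sample size and analysis do not change.

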11.1 Tissue biopsies

- In patients with disease that can be safely biopsied, an attempt will be made to 11.1.1 obtain tissue before the start of treatment and prior to the start of Cycle 2. At time of biopsy, an attempt will be made to remove the equivalent of two cores or two punch biopsies. The first biopsy is to be formalin-fixed and paraffinembedded. The second sample and other additional cores if obtained are to be flash-frozen using liquid nitrogen and then stored at -70°C to -80°C for future studies (see Study Operations Manual).
- For patients who are registered at affiliate sites, patients will be given the option 11.1.2 of traveling to The Cancer Institute of New Jersey to have a tumor biopsy performed and/or correlative blood studies drawn. Patients may opt not to have

these studies done yet remain on the study. These tests can only be performed at As stated, patients may choose to come to the and have these tests performed at no cost to the them.

- Biopsies will be obtained only if they can be performed under local anesthesia. 11.1.3 General anesthesia will not be used to obtain biopsies that are to be used only for research purposes. These biopsies may be obtained with the assistance of either a surgical consultant or a member of the interventional radiology staff.
- Biopsies performed for research purposes will only be obtained after the 11.1.4 procedure has been explained to the patient and informed consent has been secured per institution policy. Patients will have the opportunity to consent or refuse the use of their tumor samples for additional unplanned studies.

11.2 Immunohistochemistry Analysis

- Tumor tissue samples (from time of original diagnosis or if not available, 11.2.1 metastatic diagnosis, or if collected on study) will be collected for each patient on-study to evaluate the expression of MAPK, phosphorylated MAPK, VEGFR-2, phosphorylated VEGFR-2, and Ki67 by immunohistochemistry.
- Paraffin blocks containing embedded tissue samples are preferred; however if a 11.2.2 paraffin block is not available 10 unstained slides should be submitted to [name] C/O [name] at the Repository Service (BRS).

Circulating Tumor Cells 11.3

In several studies it has been shown that circulating tumor cells (CTCs) can be found in the peripheral blood of patients with a variety of metastatic carcinomas. The presence of CTCs has been associated with poor prognosis in patients with metastatic breast cancer,46 and similar conclusions are likely true for other types of carcinomas. Recent studies have also identified both the prognostic and predictive utility for determining the number of CTCs in patients with metastatic breast cancer. 43,44 In addition to quantitating CTCs, these cells may provide an opportunity to characterize molecular changes in the tumor, thereby helping to guide targeted therapy. In this study, analysis of changes in the number of CTCs, pretreatment and after 2 cycles of treatment, will be performed and compared to radiological studies obtained at similar time points. Details regarding collection, handling, storage, and shipping of blood samples will be provided in the Study Operations Manual.

11.4 **Imaging Studies**

The potential role of dynamic contrast-enhanced computed tomography, or perfusion CT (pCT) in monitoring treatment with anticancer agents that affect tumor angiogenesis is evolving. pCT is a non-invasive functional imaging technique capable of assessing tumor microvasculature clinically. 45 The pCT technique is based on the continuous acquisition of 3D CT images during the distribution of an intravenously administered iodinated contrast

Phase I/II Trial of Letrozole and Sorafenib as First-Line Therapy in Postmenopausal Women with Hormone Receptor-Positive Locally Advanced or Metastatic Breast Cancer PI:

agent bolus. The contrast agent is FDA-approved and is used in routine clinical practice. The total contrast administered to each patient is within the FDA-approved limits. Perfusion CT does not involve the use of an investigational device.

In this study, pCT will be performed before treatment and after two cycles of treatment in patients who are undergoing their radiographic assessments at University Hospital. A metastatic site will be selected to assess the rate of blood flow to the tumor. All pCT examinations will be performed on the dual-source Siemens Somatom Definition CT. pCT will be performed 5 minutes following the acquisition of the standard-of-care contrast-enhanced CT. The pCT will be acquired following an additional injection of 40 ml of iodinated contrast at a rate of 4 ml/sec. The dynamic acquisition will take place at 6 time points at 3 second intervals following the contrast injection. Each image acquisition will consist of 6 slices of 5-mm thickness. Images will be transferred to a scientific workstation for analysis using the DICOM protocol. Blood flow to the lesion will be measured using the maximum-slope model. Measurement of the blood flow will include manual segmentation to exclude large blood vessels from the region of interest.

Due to resource constraints, perfusion CT (pCT) testing will not be performed on any patient in the study. As of 01/23/2013 perfusion CT (pCT) testing has been removed from the study evaluations table (see Section 6).

- 11.5 Optional and Future Studies (only for Cancer Institute of New Jersey patients)
- 11.5.1 All study participants at the provide a blood sample for retrospective genotyping. Participation in pharmacogenetic studies will be optional for all patients entering the study. A patient's acceptance of pharmacogenetic analyses will not be a requirement of their participation in the main study. See Study Operations Manual for details of sample labeling, collection, transport, and storage.
- 11.5.2 All study participants at the provide a blood sample for future unplanned studies before treatment and after two cycles of treatment. Participation will be optional for all patients entering the study. A patient's acceptance of unplanned future analyses will not be a requirement of their participation in the main study. Patients will have the opportunity to consent or refuse the use of these samples for additional unplanned studies. See Study Operations Manual for details of sample labeling, collection, transport, and storage.

